## **Background**

Lumbar puncture (LP) with spinal fluid analysis (CSF analysis) is a common procedure at neurological clinics. At the neurology clinic in Umeå, about 250-300 LP is carried out every year at a specialized LP lab, and an additional 50 LP at the ward (usually on on-call time when the LP-lab is closed). Common indications include suspected bleeding, infection, inflammation, neurodegenerative processes and CSF pressure measurement.

A relatively common complication after LP is post-LP headache (PLPH). This complication occurs in between 20 and 30% of all who have undergone an LP. It is characterized by being positional, i.e. worsens in standing (within 15 minutes after standing up) and improves/completely resolves upon lying down (within 15 minutes after lying down). PLPH occurs within 5 days of LP, and disappears within 1 week of occurrence. The headache is often associated with one of the following: neck stiffness, tinnitus, mildly impaired hearing, photosensitivity, nausea. (See International Headache Society's definition: <http://ihs-headache.org>). It is not known today why PLPH occurs, but a commonly adopted theory is that there is a leakage of CSF through the hole that has been made, which thus causes low hydrostatic pressure in the central nervous system (CNS). This either causes a painful vasodilation of veins within the CNS or traction of the pain-sensitive meninges, or both. Recommendations for relieving PLPH usually include bed rest (when PLPH has occurred - there is no evidence that bed rest prevents the occurrence of PLPH), fluid intake, caffeine intake and common analgesics. As a curative treatment in difficult-to-treat cases, one may administer a bloodpatch, which means that 15-20 ml of autologous blood is injected into the epidural space, preferably at the same level as the original LP. This is believed to have the effect of both clogging the leaking hole (platelet plug), and exerting a pressure on the spinal cavity, which increases the pressure in the CNS and thus reduces the effect of the lost amount of CSF.

During a review of diagnoses at the neurology clinic at Norrland University Hospital (NUS) between 01/01/2006 and 30 June 2012, we found on average 7.8 cases of PLPH (G97.0 - leakage of spinal fluid after LP) per year, and about 6 care days per year. An inpatient day costs SEK 7713, which means a total cost for care days of approximately SEK 50,000. This only includes the worst cases PLPH. Many more episodes of PLPH are likely to occur without being noted by the health care, and we don't know how many sick leave days/year occur due to PLPH.

It is possible to reduce the risk of PLPH. The American Academy of Neurology (AAN) notes that there is strong scientific support (class 1 evidence) that:

1. Needle size is important. The smaller the needle, the less PLPH.

2. A cutting needle should be inserted with the cutting edge parallel to the dural fibers to reduce the incidence of PLPH.
3. Non-cutting needles (atraumatic) reduce the risk of PLPH, as compared to cutting needles of the same size.
4. Re-insertion of the stylet into an atraumatic needle before needle withdrawal reduces the risk of PLPH. However, this has only been shown in one study. It has not been studied if PLPH can be prevented by reinserting the stylet in cutting needles.

In recommendations published in Läkartidningen (LT) 2008, it appears that a thin non-cutting needle (0.4 mm / 27G) works well in a neurologist clinic in Stockholm. Despite this, and despite the strong recommendations issued by AAN as stated above, it is still common that large (0.9 mm/20G), cutting needles are used at our clinic (personal communication, LP assistants, 2013). One factor that can affect the propensity to use atraumatic needle is the price: one needle costs about 50 SEK compared to a cutting needle that costs about SEK 10. Interestingly enough, the recommendation to reinsert the stylet into non-cutting needle is not included in the article in the LT, even though the AAN recommendations are very clear on this matter. This suggests that one single study is not accepted as evidence enough to change practice, and justifies that we study this in our study.

Other factors that may affect the risk of PLPH are the patient's age, BMI, sex, LP position (sitting/lying down), CSF volume drawn and if the LP is "traumatic" (i.e., associated with blood-mixed CSF).

### **Purpose and method**

The purpose of this study is to investigate how three different needles work with regard to usability, time efficiency and PLPH incidence in the clinic. The needles included are:

1. Sprotte 25G (0.5 mm) atraumatic with introducer
2. Sprotte 22G (0.7 mm) atraumatic with introducer
3. Spinocan 25G (0.5 mm) cutting

Rationale for the choices of needles: If the PLPH incidence is already low when using cutting 25G needle, and does not significantly decrease when using the same size atraumatic needle, it may be health economically reasonable to choose the former because of lower price and no need to anesthetize before insertion (the needle is not thicker than the anesthetic needle, and it is mainly penetration of the skin that feels uncomfortable). The larger (22G) atraumatic needle is included to examine the time saved (higher flow rate) when using it, and how much the PLPH incidence differs between it and the smaller one. If the PLPH incidence is very low already when using this larger needle, it can be argued not to go down further in size, as long as the time saving is large.

We also investigate whether reinserting the stylet before needle withdrawal reduces the frequency of PLPH by randomizing between reinserting it, or not, in all needle categories. Thus, there will be 6 different categories (3 needles x 2 stylet options). The patients will be randomized to either option using a computer program that block-randomizes (12 subjects/block, 2 of each needle/stylet category in each block). Randomization will occur stratified by gender, BMI above or below 25 and age over and below 50 years. This is to

ensure an even distribution of these baseline characteristics across each needle/stylet category. People who undergo LP at the neurological clinic, NUS during a 3-year period (from January 1, 2014 - December 31, 2016), and who are judged to be able to answer the follow-up questions, will be asked about participation. Data is collected during the LP itself, and at a follow-up telephone call by a blinded nurse at the neurology outpatient clinic 5 days after LP, repeated after 5 days if still having PLPH. The more exploratory parameters that are investigated are whether the opening CSF pressure is important for the risk of PLPH, and whether the volume of CSF drawn is of importance for the risk of PLPH. In addition to this, data on the intensity of the headache as well as possible sick leave are registered. As a welcome side effect of the study, we also hope that the use of small non-cutting needles increases in the clinic with reduced occurrence of PLPH as a result. A challenge lies in instructing medical student who perform many of our LPs in the use of these needles, and this parameter is also interesting to study. One of the strengths of the study is that the setting is "real life" with several different operators, supervision of medical students and an unselected patient material. We believe this may increase the external validity of the study results.

In parallel with the study, an anonymous, web-based questionnaire will be distributed via e-mail to the members of the Swedish Neurologist Association. In this questionnaire, the respondent's current approach to routine lumbar puncture (needle type, size, stylet reinsertion or not, and knowledge of AAN's guidelines) is requested. These data, together with the study results, will form the basis for health-economic calculations on various lumbar puncture strategies in Sweden, and will be used primarily in connection with the study results being reported in the form of a debate entry in e.g. Läkartidningen.

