#### Power

Since the project's results can have immediate effects on how LP is performed both nationally and internationally, we have chosen to perform an interim analysis after 2 years of study duration (1/1 2016). If clear results appear already then, the project will be interrupted. If the study runs for the full 3 years, it is estimated to include approximately n = 900 patients. These will be randomized so that approximately n = 150 ends up within each needle / stylet category (n = 300 / needle). In power calculations we assume an alpha = 0.05, power = 80%, a chi-2 test to show differences between the groups, and 900 participants. With regards to the difference between needles, it has previously been shown that LP with a non-cutting needle (22G) gave a PLPH incidence of 12.2%, compared to cutting (22G) 24.4%. To detect this difference, power calculations suggest n = 157 individuals in each group (we will have n = 300 after 3 years, n = 200 after 2 years). The difference in PLPH frequency between reinserting the stylet or not was 5% vs. 16% with a non-cutting 21G needle. Such a difference would require n = 121 patients in each group (we will have n = 450 after 3 years, n = 300 after 2 years). Size: The frequency PLPH with 24–27G needle is 5–12%, and for needles in sizes 20–22G 20–40%. To detect the smallest possible difference (20% vs. 12%) we would need n = 329 patients (we will have n = 300 after 3 years, n = 200 after 2 years).

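### The rationale for the 25G cutting needle counts a non-significant difference as support for choosing it; the confidence interval for the difference should carry that argument instead

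*Combined protocol and SAP*

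**What the plan says.** The Purpose and method section explains why each needle was included. For the 25G cutting needle it sets two joint conditions. The first is "If the PLPH incidence is already low when using cutting 25G needle", with no figure for low. The second is that incidence "does not significantly decrease when using the same size atraumatic needle, it may be health economically reasonable to choose the former because of lower price". If both hold, the conclusion is tentative and has two grounds: "it may be health economically reasonable to choose the former because of lower price and no need to anesthetize before insertion".

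The price ground comes from Background: "one needle costs about 50 SEK compared to a cutting needle that costs about SEK 10". The same Purpose and method section says that survey data and trial results together "will form the basis for health-economic calculations on various lumbar puncture strategies in Sweden".

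The only test named is in Power, as an assumption of the sample-size calculation: "a chi-2 test to show differences between the groups", with alpha 0.05 and 80% power. The needle-type calculation there rests on an earlier randomised comparison of 22G needles: "LP with a non-cutting needle (22G) gave a PLPH incidence of 12.2%, compared to cutting (22G) 24.4" (per cent). It gives 157 per group, against 300 per needle expected after three years. For small needles the section says "The frequency PLPH with 24–27G needle is 5–12" (per cent), but uses this range only for the size comparison and does not split it by tip type. No confidence-interval criterion, acceptable difference or break-even is given anywhere.

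**The concern.** A chi-square test that fails to reject says the data are compatible with no difference. They may be just as compatible with a difference large enough to matter. Using the failure to reject as a support for the cheaper needle treats these two situations alike.

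The problem is sharpest in the setting the rationale describes. If the cutting needle's incidence is low, the absolute difference available is small and the test has less chance of finding it. The first condition therefore makes the second easier to meet, even when the atraumatic needle truly halves the rate. The planned sample size gives no protection here, because its inputs are a cutting rate of 24.4% and a 12.2-point difference.

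At stake is the reading of the 25G cutting versus atraumatic comparison and what passes into the health-economic calculations. Those need the size of the difference and its uncertainty, which a significance verdict does not supply.

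**Working it through.** **Inputs.** From Power: two-sided alpha 0.05 (sidedness is not stated, but two-sided reproduces the plan), 80% power, 300 per needle, rates of 24.4% and 12.2% for 22G, and 5–12% for 24–27G. From Background: needle prices SEK 50 and SEK 10; 7.8 coded cases and about 6 care days per year at SEK 7713 per day. Assumed: all true 25G rates below.

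**1. The plan's own figure.** n = [1.96·√(2p̄(1−p̄)) + 0.8416·√(p₁q₁ + p₂q₂)]² / (p₁−p₂)², with q = 1−p. For 0.244 and 0.122, p̄ = 0.183:

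- (1.96 × 0.5468 + 0.8416 × 0.5400)² / 0.122² = 2.329 / 0.01488 = 156.5, so 157, as stated.
- At 300 per needle, power for that difference is about 97%.

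**2. Chance of a non-significant result when incidence is low.** Uncorrected two-sided chi-square, 300 per needle, exact binomial enumeration; last column from the formula in step 1.

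| Assumed cutting vs atraumatic | P(non-significant) | n per needle for 80% power |
|---|---|---|
| 12% vs 6% | 26% | 356 |
| 10% vs 5% | 34% | 435 |
| 5% vs 2.5% | 63% | 906 |

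The 2.5% rate lies below the quoted range. The normal approximation gives 27%, 36% and 64%.

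**3. Two results with the same cutting rate (8%), both non-significant.** 95% CI = d ± 1.96·√(p₁q₁/300 + p₂q₂/300).

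- 24/300 vs 24/300: d = 0; 1.96·√(2 × 0.08 × 0.92/300) = 4.3 points; CI −4.3 to +4.3.
- 24/300 vs 13/300: d = 8.00 − 4.33 = 3.67 points; z = 1.87, p = 0.062; standard error 1.96 points; CI −0.2 to +7.5.

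Because the cutting rate is identical, the low-incidence condition cannot separate these two. Both meet the second condition.

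**4. What the plan's cost figures can say.** The price gap is 50 − 10 = SEK 40.

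- In the second result, needle price per headache avoided is 40/0.0367 = SEK 1,091 at the point estimate and 40/0.0751 = SEK 533 at the upper limit. The lower limit shows no benefit.
- Inpatient cost: 6 × 7713 = SEK 46,278 per year; 46,278/7.8 ≈ SEK 5,900 per coded case.
- If every headache cost that much, break-even would be 40/5,933 = 0.7 points.
- If the same sum were spread over all headaches, assuming 20–30% of 300–350 punctures a year (60 to 105 cases), the cost is 46,278/105 to 46,278/60 = SEK 441 to 771 per case, and break-even is about 5 to 9 points.

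These break-evens leave out sick leave, outpatient care and the saving on anaesthesia. The range of 0.7 to 9 points is wide enough that the plan's figures do not settle which side of break-even the second result falls on.

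**5. Precision with equal rates at 300 per needle.** 1.96·√(2p(1−p)/300): 3.5 points at 5%, 4.3 at 8%, 4.8 at 10%, 5.2 at 12%.

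**The case against.** The strongest reply is that this is a rationale for including an arm, not an analysis rule. It says only that a choice may be reasonable, it does not name the test, and nothing confines the health-economic work to a significance verdict. That is right, and it limits the point. A reader might infer that the trial commits itself to adopting the cutting needle on a null result; the text does not say so. But no fuller rule elsewhere replaces this reasoning. If the word for significance was meant in a non-statistical sense, it has no stated size either.

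Second, the conditions are joint. A reader might infer that all non-significant results count equally for the cutting needle. They do not: the first condition can separate results with different cutting rates, and a low cutting rate caps the possible benefit. What stands is narrower: among results judged low, the second condition does not distinguish a CI centred on zero from one reaching 7.5 points.

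Third, a reader might infer that the sample size is wrong or that every null result is uninformative. Neither follows. The 157 is correct on its inputs, 300 exceeds it, and some null results would be reassuring.

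Fourth, it would go too far to say the documents contain no cost per case. Background supports a partial inpatient figure, and on one way of spreading it the 3.7-point example lies below break-even. That stands, so any judgement of which results are reassuring depends on a difference the investigators must set.

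Finally, the assumed rates are illustrative. This is conceded: the 5–12% range is not split by tip type.

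**Conclusion.** The concern holds as a fault in one inference. Failing to find a significant decrease is used as one of two supports for a tentative preference, and it cannot show that the 25G needles have similar headache rates. The 22G-based calculation does not repair this, because its rates do not describe a needle whose incidence is already low.

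Under the assumed rates, a true halving would pass as no significant decrease in roughly a quarter (12% vs 6%) to just under two thirds (5% vs 2.5%) of trials at 300 per needle. These figures illustrate the problem; they do not predict the trial's result. The lack of a number for low incidence is a missing detail and secondary to the inference itself. Whether a given difference changes the economic conclusion cannot be settled from the documents, since the partial inpatient cost leaves the break-even undetermined.

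**What to change.** In the arm rationale, replace the no-significant-decrease condition with a reading of the 95% CI for PLPH incidence, 25G cutting minus 25G atraumatic:

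- Before seeing the data, the investigators state the largest difference they would accept given the savings on price and anaesthesia. The value is theirs to choose.
- Call the needles similar only if the upper limit of the CI is below that difference. Otherwise report a non-significant result as inconclusive.
- Carry the estimate and its CI into the health-economic calculations, with needle price and the anaesthesia difference as inputs. Show any break-even based on the Background inpatient figures as a range, with its assumptions.
- If the low-incidence condition is kept, give it a number at the same time.

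The cost is some wording and one acceptable difference to agree; no new patients or data. The downside is more results reported as inconclusive. Even with equal observed rates, the upper limit would be about 3.5 points at 5% incidence and 5.2 points at 12%, so a smaller acceptable difference could not be shown by equal rates at 300 per needle.

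### The stylet effect is sized only as one comparison pooled over three needles, from a non-cutting needle's rates, and no separate estimate is described for the cutting needle

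*Combined protocol and SAP*

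**What the plan says.** Under Purpose and method, patients are randomised to three needles (Sprotte 25G and 22G, both atraumatic, and Spinocan 25G, cutting) crossed with reinserting the stylet or not. Blocks of 12 hold two patients per cell. The stylet question is "whether reinserting the stylet before needle withdrawal reduces the frequency of PLPH by randomizing between reinserting it, or not, in all needle categories".

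The Power section gives one calculation for it. The difference "between reinserting the stylet or not was 5% vs. 16% with a non-cutting 21G needle" is the input, followed by "Such a difference would require n = 121 patients in each group (we will have n = 450 after 3 years"; the figure at 2 years is 300. It also states that "approximately n = 150 ends up within each needle / stylet category (n = 300 / needle"), but attaches no stylet comparison to those cells. An interim analysis follows at 2 years: "If clear results appear already then, the project will be interrupted".

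The Background ties the existing recommendation to atraumatic needles and adds: "It has not been studied if PLPH can be prevented by reinserting the stylet in cutting needles".

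On use of the results, Purpose and method says that they, with a questionnaire on needle type, size and stylet practice, "will form the basis for health-economic calculations on various lumbar puncture strategies in Sweden". Of the cutting 25G needle, should its headache rate prove low, it says "it may be health economically reasonable to choose the former because of lower price".

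The only test named is a chi-square, as an assumption for the power calculation. Randomisation is stratified by sex, BMI and age, which the Background lists among factors that may affect post-LP headache (PLPH).

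**The concern.** A third of the patients in the pooled stylet comparison receive a cutting needle, for which the plan has no prior evidence on reinsertion. The rates used to size the comparison come from the other needle type. If reinsertion helps in atraumatic needles only, a pooled result averages a real effect with none. It would probably still be significant, and it would be the wrong size for both needle types.

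At stake is the advice on reinsertion for users of the cheaper cutting needle, and the stylet effect entered for each needle in the health-economic work. The question is sharper at 2 years, when numbers are smaller and the project may be stopped.

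**Working it through.** **1. The plan's own figure.** Inputs from the Power section: 5% vs 16%, alpha 0.05 (two-sided, an assumption that reproduces the figure), power 80%.

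n = [1.96·√(2·p̄·q̄) + 0.8416·√(p1·q1 + p2·q2)]² / (p1 − p2)²

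With p̄ = 0.105: 2·p̄·q̄ = 0.18795, and p1·q1 + p2·q2 = 0.1344 + 0.0475 = 0.1819. So n = (0.8497 + 0.3589)² / 0.0121 = 120.7, i.e. **121 per group, as stated**. The same formula gives the plan's 157 and 329 for its other comparisons. Power for 5% vs 16% with 450 per group is 99.97%.

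**2. Cell sizes.** At 3 years there are about 150 per cell: 300 vs 300 for stylet in the two atraumatic needles and 150 vs 150 in the cutting needle. At 2 years, 300 per stylet arm over three needles gives 100 per cell: 200 vs 200 and 100 vs 100.

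**3. Scenario (assumed).** Atraumatic needles: 16% vs 5%. Cutting needle: no stylet effect, at a rate c. I took c from 5% to 24.4%. The Power section gives 5–12% for 24–27G needles (not split by tip), 16% for the non-cutting 21G needle without reinsertion, and 24.4% for a cutting 22G needle.

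Pooled rates are (2·16% + c)/3 vs (2·5% + c)/3. The difference is 22/3 = **7.3 points** whatever c is. It overstates the cutting effect by 7.3 points (73 per 1,000 patients) and understates the atraumatic effect by 11 − 7.3 = 3.7 points.

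**4. What the tests would show.** These come from 400,000 simulated trials per row, each test at an unadjusted two-sided 5% because the plan names no interim boundary. The interaction is a 1-df Wald test of atraumatic vs cutting, with 0.5 added per cell on log-odds. Entries are percentages of trials, at 3 years / 2 years unless marked.

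| Cutting rate c | Pooled test significant | Interaction significant, log-odds | Interaction significant, risk difference (3 years) | Log-odds interaction non-significant, given pooled significant |
|---|---|---|---|---|
| 5% | 98 / 91 | 56 / 40 | 88 | 44 / 60 |
| 12% | 95 / 83 | 78 / 61 | 69 | 22 / 40 |
| 16% | 92 / 79 | 84 / 66 | 62 | 16 / 34 |
| 24.4% | 88 / 72 | 89 / 74 | 51 | 11 / 27 |

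A closed-form check of the pooled test at c = 24.4% (18.8% vs 11.5%, 450 per group) gives 86.8%, in line with the last row.

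Neither scale is stronger throughout. Risk difference does better at 5% and 8% (79% vs 69% at 8%, 3 years), log-odds at about 12% and above. If the cutting needle had half the log-odds effect rather than none, log-odds interaction power would be only 27–31% at 3 years and 19–22% at 2 years (c from 16% to 24.4%).

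**5. Precision of separate estimates.** The 95% CI half-width is 1.96·√[(p1·q1 + p2·q2)/n].
- Cutting, equal rates: n = 150 gives 4.9 points at c = 5%, 7.4 at 12%, 8.3 at 16% and 9.7 at 24.4%. n = 100 gives 6.0, 9.0, 10.2 and 11.9.
- Atraumatic, 16% vs 5%: 4.8 points (n = 300) and 5.9 (n = 200).

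**6. Power within the cutting needle.** If 16% vs 5% carried over, power would be 87.8% with 150 per group and 72.1% with 100. With the same relative risk (5/16 = 0.3125) and 150 per group, it is 39% at a rate of 5% without reinsertion, 67% at 10% and 76% at 12%.

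**7. Adjustment (minor).** Simulations of the planned stratified blocks assumed stratum odds ratios from 1 to 3 and compared Cochran-Mantel-Haenszel over strata and stylet with the plain chi-square. For the 20% vs 12% needle-size comparison, power changed by −0.2 to +4.1 points. The type I error of the plain test was 5.0% at odds ratios of 1, 4.4–4.6% at 2 and 3.9–4.0% at 3, so it is valid and slightly conservative.

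**The case against.** The strongest reply is that pooling over needles is the ordinary main-effect analysis of a factorial trial, and that all six cells stay identifiable, so by-needle reporting is not excluded. That is correct, and the pooled test should stay. The gap remains: by-needle estimates chosen after the data are seen are post hoc, and nothing in the plan says how the result will be read for the cutting needle.

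A second reply is that the plan never promises a stylet effect by needle. Its stated reason for studying reinsertion is that a single study has not changed practice, and its price argument concerns headache by needle, not by stylet. This stands in part. The need for a by-needle effect is a reasonable inference from the Background and from Purpose and method, not a stated requirement.

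Third, the documents describe no final analysis for any comparison, so the gap is not peculiar to stylet. True, but here the plan itself names the unstudied subgroup and randomises within it.

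A reader might infer that the cutting-needle comparison is adequately powered, because 150 per cell exceeds 121. The documents do not support this: 121 rests on rates from a non-cutting 21G needle, and carrying them to a cutting 25G needle is the very borrowing at issue.

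**Conclusion.** The point holds as a gap in the planned analysis. Stylet reinsertion is randomised within every needle but sized once, over all needles, from a non-cutting rate, with no separate estimate described for the cutting needle. In the assumed scenario the pooled test would be significant in 98–88% of trials at 3 years and 91–72% at 2 years, while misstating the effect by 7.3 points in one direction and 3.7 in the other. The size depends on that scenario, since the documents give no cutting-needle stylet figure. The design can supply a cutting-needle estimate, but an imprecise one: about ±5 to 10 points at 3 years and ±6 to 12 at 2 years.

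Three stronger readings are not supported. The stylet sample size is not wrong: 121 reproduces and 450 far exceeds it. The plan does not neglect needle tip in general: it plans and sizes cutting against non-cutting needles, and what is absent is needle type within the stylet question. The plain chi-square is not invalid, nor is it fixed as the final method; adjustment is a matter of efficiency only.

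This should be changed, though it does not threaten the trial's validity.

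**What to change.** Pre-specify the following.

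1. The stylet risk difference with 95% CI, separately for the atraumatic needles (22G and 25G together, about 300 vs 300) and the cutting needle (about 150 vs 150), beside the pooled comparison, which remains the one stylet test.
2. Conclusions about cutting needles rest on their own estimate and CI.
3. Any stylet-by-needle-type interaction test is supportive only, with 1 df and on one scale named in advance. A non-significant interaction does not extend the pooled result to cutting needles, above all at the 2-year interim.
4. As a separate minor improvement, analyse the main comparisons by logistic regression with needle, stylet, sex, BMI group and age group, or by Cochran-Mantel-Haenszel over the strata and the other factor. Report an adjusted risk difference with 95% CI and keep the plain chi-square as a sensitivity analysis.

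The cost is protocol wording and a little analysis work, with no extra patients or data. The by-needle results are estimates, so no alpha is split. The plan should say openly that the cutting-needle interval will be wide and that power there is not established. Adjustment loses about 0.2 points of power or less if the strata are not prognostic.

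### A fixed block of 12 in each stratum, with operators who see the needle and no described concealment step, leaves some allocations predictable in principle

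*Combined protocol and SAP*

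**What the plan says.** All references are to the combined protocol and SAP.

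- **Allocation (Purpose and method).** "The patients will be randomized to either option using a computer program that block-randomizes", with "12 subjects/block, 2 of each needle/stylet category in each block". No other block size is mentioned.
- **Strata (same section).** "Randomization will occur stratified by gender, BMI above or below 25 and age over and below 50 years", which makes 2 × 2 × 2 = 8 strata.
- **Entry (same section).** Patients "who are judged to be able to answer the follow-up questions, will be asked about participation". The text does not say who makes that judgement.
- **Blinding (same section).** Only the follow-up assessor is called blinded: data come "at a follow-up telephone call by a blinded nurse at the neurology outpatient clinic 5 days after LP". Nothing is said about the operator or LP assistants, but the person doing the puncture cannot be unaware of the needle or of stylet reinsertion.
- **Setting.** Under Background, "about 250-300 LP is carried out every year at a specialized LP lab", plus some 50 a year on the ward. Purpose and method describes "several different operators, supervision of medical students". Under Budget, LP assistants and assistant nurses collect the data as part of their ordinary work, and a scale and measuring stick are to be bought.

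The document does not say who runs the program, whether consent and stratum entry come before the allocation is shown, or whether the block size is withheld from clinic staff.

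**The concern.** In a block of known size and composition, the allocations already used determine what is left. When the people who see past allocations also work where patients are recruited, the end of a block can be worked out, and the decision to enrol can then depend on the coming allocation. The blinded telephone nurse protects outcome assessment, not entry.

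At stake is the comparability of the arms. The protocol itself lists CSF volume and traumatic puncture among factors that may affect post-LP headache, and neither is a stratification factor. It also includes the 22G needle for its faster flow, so staff could have a reason to prefer one needle for some patients. If enrolment did depend on the expected needle, headache incidence, procedure time and usability could all be distorted.

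**Working it through.** **The plan's own figures.** The plan gives no figure for predictability. Its sample sizes under Power (157, 121 and 329 per group) reproduce exactly with a two-sided alpha of 0.05, 80% power, pooled variance and no continuity correction. Nothing below changes them.

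**Inputs.** Block of 12, with 2 of each of 6 categories, so 4 of each needle and 6 of each stylet option (Purpose and method). Eight strata. 900 patients over 3 years (Power).

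**Upper-bound assumption.** An observer knows the block size, knows where each block starts, and has an error-free tally for each stratum.

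**Certain allocations.** The k-th place from the end is certain when the last k places all hold the same option. The expected number of certain places per block is the sum of those probabilities.

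*Needle*, terms 3 × C(4,k)/C(12,k):
- k = 1 (place 12): 1
- k = 2 (place 11): 18/66 = 0.273
- k = 3 (place 10): 12/220 = 0.055
- k = 4 (place 9): 3/495 = 0.006
- Sum 1.333 of 12 = 11.1%; 900 × 0.111 = about 100 patients. The last place supplies 1/1.333 = 75% of this.

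*Stylet*, terms 2 × C(6,k)/C(12,k):
- k = 1 to 6: 1, 0.455, 0.182, 0.061, 0.015, 0.002
- Sum 1.714 of 12 = 14.3%; 900 × 0.143 = about 129 patients. The last place supplies 1/1.714 = 58%.

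*Exact category of six*: 1 + 6/66 = 1.09 of 12 = 9.1%, about 82 patients.

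Simulation of 60,000 blocks agrees (11.1%, 14.3% and 9.1%).

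**Average guessing success under the same tracking.** Needle 51% (33% by chance); stylet 64% (50% by chance).

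**How hard the tracking is.** With equal strata (an assumption), 300 patients a year / 8 = 37.5 per stratum per year, so a block stays open 12/37.5 × 12 = 3.8 months.

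**If the BMI stratum is not yet known.** Both candidate strata must be certain and point to the same option. Treating them as independent, this is 0.111 × 0.111 / 3 = about 0.4% for needle and 0.143 × 0.143 / 2 = about 1.0% for stylet.

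**Effect of varying the blocks.** Simulated with about 112 patients per stratum (900/8), sizes 6, 12 and 18 drawn at random, and a tracker who knows that set of sizes: needle allocations known with certainty fall from about 11% to about 3%. Average guessing success moves only from about 51% to about 50%, because guessing the needle used least so far needs no knowledge of block size.

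**The case against.** The other side has a strong case, and much of it stands.

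- **The figures are a ceiling.** Nothing says that LP staff know the block size or hold a list of past allocations. They would need to tally eight interleaved strata for nearly four months, across several operators and ward punctures. This stands.
- **Deduction before approach.** A reader might infer that staff can deduce the allocation before approaching a patient. The documents do not show this. BMI is a stratum factor and equipment is bought to measure it, so the stratum may be unknown until then, unless BMI is on record or evident by eye.
- **The 51% and 64% as a measure of harm.** A reader might take these as the size of the problem. For avoidance of 25G needles they are the wrong figures: two of the three needles are 25G, so the next is 25G 67% of the time without any tracking. Perfect tracking raises best-guess success on gauge to only 72%. 25G is certain for 8/5 = 1.6 of 12 places, or 13%.
- **Selection is conjecture.** The entry criterion concerns answering follow-up questions, not puncture difficulty. Deferral is implausible for suspected bleeding or infection. The plan expects about 900 patients from 3 × 300 = 900 to 3 × 350 = 1,050 punctures, which leaves little room for selective exclusion if that target is met.
- **The program already needs the stratum.** True of any stratified allocation. It does not establish that eligibility and consent are fixed first, or that an entry cannot be withdrawn once the allocation is seen.

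What remains is a stated fixed block size, unavoidable operator knowledge, discretionary entry and no described safeguard. A block of 12 for six arms is a common choice and only its last place is always certain, but here nothing offsets that weakness.

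**Conclusion.** The point holds as a minor, cheaply removed risk to allocation concealment. At most about 11% of needle allocations (about 100 of 900) and 14% of stylet allocations (about 129 of 900) could be known with certainty. That bound rests on a known block size, error-free tracking and a known stratum; with the BMI stratum unknown it falls to about 0.4% and 1.0%.

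A reader might go further and conclude that concealment fails or that the comparison is biased. The documents do not support that. Silence on concealment is a gap in description, no selective enrolment is shown, and no effect on headache incidence has been estimated. Nor would any such bias necessarily be beyond examination: CSF volume and opening pressure are recorded, and the last places of blocks could be left out as a sensitivity check.

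**What to change.** 1. Have the program vary block size at random in multiples of 6 within each of the eight strata, for example 6, 12 and 18.
2. Keep the sizes out of the version of the protocol that clinic staff use, and state who sets up the program and holds the sequence.
3. Require eligibility, consent and stratum (including measured BMI) to be entered irrevocably before the program shows the allocation.

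Step 1 removes most of the certainty but hardly changes average guessing success, so step 3 should not be treated as optional. If steps 2 and 3 are already practice, stating them would settle most of the point.

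The cost is a program setting and a short protocol amendment; the sample sizes are unaffected. The downside is a marginally larger possible imbalance within a stratum at the interim and final analyses.
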